#### Statistical Methods:

Sample size calculation: The sample size for this study is not based on statistical considerations but is typical for studies of this nature and is considered adequate to characterize the distribution of the planned endpoints. Any statistical testing will be considered exploratory and descriptive.

Analysis sets:

- Safety Evaluation Population: All subjects randomly assigned to the IP and who take 1 dose of IP. Subjects will be analyzed according to the treatment they received.
- DLAE Evaluation Population: All subjects who received 1 dose of IP and completed the 15-day DLAE follow-up period.
- PK Evaluation Population: All subjects who received at least 1 dose of JK07 and have at least 1 quantifiable JK07 plasma concentration collected postdose without important protocol deviations/violations or events thought to significantly affect the PK results.
- Exploratory PD/biomarker Evaluation Population: All subjects who take 1 dose of IP and have at least 1 exploratory PD variable or biomarker endpoint collected postdose without important protocol deviations/violations or events thought to significantly affect the PD results.

Safety Analyses: All data will be provided in data listings sorted by treatment group, subject number, and visit. Summary data will be presented in a tabular format by treatment group, by scheduled time point, visit, and overall (as appropriate). Categorical data will be summarized by the number and percentage of subjects in each category. Continuous data will be summarized by descriptive statistics including at a minimum sample size (n), mean, standard deviation, median, minimum, and maximum. Change from baseline will be calculated as value postdose subtracted by value at baseline. The baseline measure will be defined as the last non-missing measure prior to initiation of the IP. Outliers for QT and QTc defined under outcome measures will be summarized using cumulative counts and percentages by treatment and sampling time, if appropriate. Abnormal findings on 12-lead ECG will be summarized by treatment using descriptive statistics.

[figure not shown]
PK Analyses: Intact JK07 concentrations, determined through detection of both the antibody domain and NRG-1 peptide, and calculated parameters will be listed and descriptively summarized by active treatment for the PK Evaluation population. Dose proportionality will be explored graphically, and, if applicable, using a power model.

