#### 4.6 Study Stopping Criteria

Intravenous administration for any individual subject will be stopped if the subject experiences a serious adverse event (SAE) or a clinically significant, drug-related AE during the infusion, which in the opinion of the study physician, Principal Investigator, or Sponsor's medical representative, warrants discontinuation of the study for that subject's well-being. The definitions of an AE and an SAE can be found in [Section 8.3](#).

The final determination of whether any AE observed following JK07 administration is considered dose-limiting will be at the discretion of the DRC. Guidance provided to the DRC will be to view as a possible DLAE any AE at least possibly related to IP that results in any new finding of the following if observed within the first 15 days of treatment (DLAE assessment period):

- Any febrile neutropenia [absolute neutrophil count (ANC)]  $<1000/\text{mm}^3$ , temperature  $>38.3\text{ }^{\circ}\text{C}$  ( $101\text{ }^{\circ}\text{F}$ ) for  $>1$  hour.
- Any signs and/or symptoms of myocardial ischemia/myocardial infarction (diagnosis to be based on Thygesen et al. 2018), and any asymptomatic/symptomatic significant ( $> 2$  mm for  $> 2$  minutes) new ST segment deviation (elevation or depression), as defined in Hicks et al. 2018.
- Any emergent symptomatic or asymptomatic cardiac arrhythmia requiring at least urgent medical intervention.
- Any  $\geq$  QTc(F) prolongation of  $>500$  msec or  $>60$  msec above baseline (based on an average QTcF value of triplicate ECGs).
- Any emergent  $\geq$  severe (corresponding to CTCAE v5 Grade 3) hematologic, non-hematologic, hepato-cellular, or renal toxicity except for untreated nausea, diarrhea, vomiting, constipation, abdominal pain. Any of these will be considered DLTs if persisting  $>72$  hours despite appropriate treatment.
- Any at least moderate CD4 lymphocyte count  $\leq 400\text{ mm}^3$ .
- Any at least moderate infusion-related reaction or inability to deliver a complete dose due to possible treatment-related toxicity.
- An AE or SAE that, in the opinion of the DRC, is of potential clinical significance such that further dose escalation would expose subjects to unacceptable risk. In addition, the DRC may identify as a DLAE, any AE that impairs daily function, or abnormality occurring in subjects treated with JK07 at any time during the trial.

Each DLAE must be recorded in the eCRF.

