**Table 11 Analysis Sets**

Analysis Set	Description
Safety Evaluation Population	All subjects randomly assigned to the IP and who take at least 1 dose of IP. Subjects will be analyzed according to the treatment they received.
Dose-limiting Adverse Event (DLAE) Evaluation Population	All subjects who received at least 1 dose of IP and completed the 15-day DLAE follow-up period.
Pharmacokinetic (PK) Evaluation Population	All subjects who received at least 1 dose of IP and have at least 1 quantifiable IP plasma concentration collected postdose without important protocol deviations/violations or events thought to significantly affect the PK results.
Exploratory Pharmacodynamic (PD)/Biomarker Evaluation Population	All subjects who take at least 1 dose of IP and have at least 1 exploratory PD variable or biomarker endpoint collected postdose without important protocol deviations/violations or events thought to significantly affect the PD results.

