#### **9.4.3 Safety Analyses**

All safety analyses will be performed on the Safety Population.

All safety data will be listed according to treatment group, subject number, and visit.

The AEs are defined in [Section 8.3.1](#). The DLAE are defined in [Section 4.6](#).

AEs will be coded using the Medical Dictionary for Regulatory Activities (MedDRA) Version 22. The number of AEs and incidence rates will be tabulated by preferred term and system organ class.

The AEs will be coded by maximum severity, relationship to study treatment, as SAEs or DLTs as needed, and will be categorized and tabulated for each treatment group (cohort).

DLAEs will be presented in the same manner as the AEs.

Incidence of injection site reactions will be summarized by treatment group, and if appropriate by assessment time.

All laboratory test results, vital signs measurements, ECG results, weight, and body mass index will be summarized for each treatment group using descriptive statistics at each visit for raw numbers and change from baseline. The incidence of treatment-emergent abnormal laboratory, vital sign, and ECG values will also be summarized using descriptive statistics.

For 12-lead ECG parameters (HR, PR, QRS, QT, QTcF), the 90 % confidence interval will also be presented for each parameter mean and change from baseline values. Outliers for QT and QTcF defined under outcome measures will be summarized using counts and percentages by treatment and sampling time, if appropriate and using subject-level maximum over time by treatment. The following categories will be presented by treatment and overall, for JK07:

- outlier QT and QTcF intervals (450-480 ms, 480-500 ms and >500 ms)
- change from baseline in QT and QTcF intervals (30-60 ms and >60 ms)

Additional corrections to QT may also be similarly analyzed. If relevant, analysis excluding ECGs capturing paced beats will be performed.

Abnormal findings on 12-lead ECG will be summarized by treatment using descriptive statistics.

All recorded ECGs will be interpreted on site and subsequently collected, digitized, and sent for central laboratory standardized measurements. The incidence (number of subjects and percent) of a confirmed positive ADA response will be summarized by treatment. The incidence of neutralizing anti-drug antibody response will also be summarized, if appropriate.

All data will be provided in data listings sorted by treatment group, subject number, and visit.

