## **K. Analysis Populations**

Five (5) analysis populations will be defined for use with various analyses:

- Safety Evaluation Population: subjects who are randomized and have a dose of IP (either JK07 or placebo) administered. Subjects will be analyzed according to the treatment they received.

- Dose-Limiting Adverse Event (DLAE) Evaluation Population: all subjects in the safety population who have a dose of IP (either JK07 or placebo) administered and have completed the 15-day DLAE follow-up period (Day 1 to Day 15). Subjects will be analyzed according to the treatment they received.
- PK Evaluation Population: subjects who have a dose of IP (either JK07 or placebo) administered and have at least one quantifiable IP plasma concentration collected after dose IP administration, with no major protocol deviations which are considered to affect the PK results. This population will be used for the PK concentration data summaries and listings.
- PK Parameter Population: subjects from PK Evaluation Population who had at least 1 PK parameter of JK07 available. Subjects will be excluded from the PK analysis if they have too few serum concentration data points to allow accurate assessment of PK parameters. This population will be used for the PK parameter data summaries and listings.
- Exploratory PD/biomarker Evaluation Population: The PD population will include all randomized subjects who have a dose of IP (either JK07 or placebo) administered and have at least one post-baseline exploratory PD endpoint collected post-dose without any major protocol deviations which are considered to affect the PD results. The PD population will be used for the analyses/summaries of PD/biomarker endpoints. Subjects will be analyzed according to the treatment they received.

Criteria for major protocol deviations excluding subjects from the PK or PD evaluation population will be determined based on a blinded review of the data prior to the unblinding of the study, as defined in the Clinical Monitoring Plan. Subjects with protocol deviations affecting PK or PD results will be determined prior to the database lock.

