## **VII. Safety Analyses**

All safety analyses will be performed on the Safety Evaluation Population. Analyses specific to DLAEs will use the DLAE Evaluation Population. The subjects given placebo are also included specifically to compare against JK07 such that the background disease from the treatment effects in the study population may be assessed and better discerned. All safety data will be evaluated based on Common Terminology Criteria for Analysis Events (CTCAE) Version 5.0, and listed by cohort, subject, and visit. Categorical data will be summarized in count and percentage by cohort and category.

For laboratory test results, vital signs, ECG results, weight, and body mass index (BMI), observed values and change from baseline (CFBL) will be summarized by cohort and visit using descriptive statistics.

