- DLAEs related to study drug. This subset includes DLAEs with a drug relationship of “possibly related” and “definitely related”, or a missing drug relationship.
- Serious DLAEs
- Serious DLAEs related to study drug. This subset includes Serious DLAEs with a drug relationship of “possibly related” and “definitely related”, or a missing drug relationship.
- DLAEs leading to study drug permanent discontinuation
- DLAEs leading to study drug infusion interruption. This subset includes DLAEs with an answer “Yes” to the question “Was infusion interrupted?” on the Infusion Drug Administration form.
- DLAEs with infusion site reactions. This subset includes DLAEs with an answer “Yes” to the question “Was this an infusion site reaction?” on the AE form
- **SAEs**

In addition, summary tables will present the number and percentage of subjects and events by treatment group and overall, ordered by System Organ Class (SOC), Preferred Term (PT), and by the following classes, using the Safety Evaluation Population:

- SAEs
- SAEs having Infusion Site Reaction
- TEAEs
- TEAEs leading to study drug infusion interruption
- TEAEs leading to study drug permanent discontinuation
- TEAEs related to study drug
- TEAEs having Infusion Site Reaction
- DLAEs
- TEAEs by maximum severity (i.e. by CTCAE grading)
- TEAEs by maximum relationship to study drug

The DLAEs will be summarized by SOC and PT for the DLAE Evaluation Population.

At each level of summary of subject, a subject will be counted once if he/she reported one or more events. Specifically:

- For summary of TEAEs by severity, a subject will be classified according to the most severe event.
- For summary of TEAEs by relationship to study drug, a subject will be classified according to the closest relationship.

- For summary of SAEs by outcome, a subject will be classified according to the worst outcome.

For summary of TEAEs by action taken with study drug, a subject will be classified as “Drug Permanently Discontinued,” “Dose Interrupted,” “Other Action,” or “Dose Not changed.”

All AEs will be presented in a by-subject listing, detailing in the verbatim term given by the investigator, PT, SOC, start date, end date or ongoing, severity, seriousness, outcome, relationship to the study drug, and action taken. Treatment-emergent infusion site reactions, TEAEs leading to drug permanently discontinuation, and TEAEs related to study drug, DLAEs, SAEs, and deaths will be presented in separate listings respectively.

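### The DLAE Evaluation Population admits only Day 15 completers, so a DLAE followed by early exit drops out of one of the two planned DLAE tables

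*SAP*

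**What the plan says.** Three places define the set, all with a completion condition and none with an exception for a subject who had a DLAE:

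- SAP V.K: subjects in the safety population with a dose of IP "administered and have completed the 15-day DLAE follow-up period (Day 1 to Day 15".
- Protocol Table 11: "All subjects who received at least 1 dose of IP and completed the 15-day DLAE follow-up period".
- Protocol synopsis, Statistical Methods: "All subjects who received 1 dose of IP and completed the 15-day DLAE follow-up period".

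Protocol 4.6 treats an event as a possible DLAE "if observed within the first 15 days of treatment (DLAE assessment period", so the follow-up a subject must complete is also the window in which the outcome is assessed.

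SAP VII states: "Analyses specific to DLAEs will use the DLAE Evaluation Population". SAP VII.B repeats this for the table: "The DLAEs will be summarized by SOC and PT for the DLAE Evaluation Population". The same section also names DLAEs in a list of SOC/PT tables to be produced by treatment group "and by the following classes, using the Safety Evaluation Population", and plans a separate DLAE listing. Two SOC/PT tables of DLAEs are therefore planned, on different sets.

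The Safety Evaluation Population in SAP V.K consists of randomized, dosed subjects. SAP IV.D says that sentinel subjects are not randomized.

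**The concern.** Membership of the set can depend on the outcome it is meant to measure. A subject whose DLAE is followed by death, withdrawal of consent or loss to follow-up before Day 15 has not completed the period and is excluded together with the event. The direction is unwelcome: the events most likely to end participation are the ones left out. Safety and tolerability are the primary objective, and the SAP reports by dose level, so one exclusion can turn an observed DLAE into a displayed 0%.

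**Working it through.** **Inputs from the documents.** A standard cohort has 1 sentinel plus 4 randomized 3:1, so 3 randomized and 4 dosed JK07 subjects (SAP IV.D). An expanded cohort has 1 sentinel plus 8 randomized 6:2, so 6 randomized and 7 dosed JK07 subjects (SAP IV.A). The stated maximum of 63 is 7 cohorts × 9 subjects; the point does not depend on it. The documents give no DLAE rate and no early-loss rate, so those below are assumptions.

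**Counts for one cohort.** Assume one randomized JK07 subject has a DLAE and leaves before Day 15. The current rule drops that subject. The revised rule (DLAE in the window, or completion) keeps the subject. Rows with the sentinel assume that the sentinel is counted, completes and has no event.

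| JK07 subjects counted | Other early losses | Current rule | Revised rule | All counted subjects |
|---|---|---|---|---|
| 3:1, randomized (3) | none | 0/2 | 1/3 (33%) | 1/3 (33%) |
| 6:2, randomized (6) | none | 0/5 | 1/6 (17%) | 1/6 (17%) |
| 3:1, with sentinel (4) | none | 0/3 | 1/4 (25%) | 1/4 (25%) |
| 6:2, with sentinel (7) | none | 0/6 | 1/7 (14%) | 1/7 (14%) |
| 3:1, randomized (3) | one, event-free | 0/1 | 1/2 (50%) | 1/3 (33%) |
| 6:2, randomized (6) | one, event-free | 0/4 | 1/5 (20%) | 1/6 (17%) |
| 3:1, with sentinel (4) | one, event-free | 0/2 | 1/3 (33%) | 1/4 (25%) |
| 6:2, with sentinel (7) | one, event-free | 0/5 | 1/6 (17%) | 1/7 (14%) |

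**Expected rates.** Let p be the true DLAE probability, q the probability of early loss given a DLAE, and r the probability of early loss without one.

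- Current rule: f = p(1−q) / [p(1−q) + (1−p)(1−r)]
- Revised rule: g = p / [p + (1−p)(1−r)], which does not involve q

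Take p = 0.20 (assumed).

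- f at r = 0.1: q = 0.1 gives 0.18/0.90 = 20.0%; q = 0.25 gives 0.15/0.87 = 17.2%; q = 0.5 gives 0.10/0.82 = 12.2%; q = 1 gives 0%.
- g: r = 0 gives 20.0%; r = 0.05 gives 0.20/0.96 = 20.8%; r = 0.1 gives 0.20/0.92 = 21.7%; r = 0.2 gives 0.20/0.84 = 23.8%.

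The current rule recovers p when q = r and falls below it when q > r. The revised rule is at or above p for every r. Setting p − f = g − p gives the q beyond which the revised rule is the closer: about 0.10 at r = 0.05, 0.20 at r = 0.1 and 0.38 at r = 0.2.

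**Sentinels.** The SAP nests the DLAE set in a Safety Evaluation Population of randomized subjects. Read literally, a sentinel's DLAE is outside both SOC/PT tables, even if the sentinel completes Day 15. Protocol Table 11 defines the DLAE set by dosing, without a randomization condition. Adding an exception for DLAEs while keeping the SAP's nesting would leave that gap open.

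**The case against.** The best defence is that little depends on this table. The same DLAE, in a randomized subject, appears in the Safety-population table in the same SOC/PT layout, and DLAEs have their own listing. No formal testing is planned. The trigger is narrow: this is a single-dose study, stopping an infusion does not end participation, and Protocol 7.2 asks that subjects withdrawing because of an AE be followed up. That leaves death, withdrawal or loss within about two weeks of dosing. The revised rule is also not uniformly better, since the current rule is unbiased when early loss is equally likely with and without a DLAE. All of this stands, and it sets the severity. It does not remove the gap in the definition.

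A reader might infer that the SAP departs without record from Protocol 9.4.3, which states: "All safety analyses will be performed on the Safety Population". The documents do not support that. The protocol itself creates the DLAE set in Table 11 and the synopsis, and the SAP's Safety-population DLAE table meets 9.4.3. At most, 9.4.3 and Table 11 sit awkwardly together within the protocol. Nor does the general missing-data rule in Protocol 9.4.5 establish a conflict: it does not amend the population definitions, and AEs of withdrawn subjects enter the Safety-population tables.

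**Conclusion.** The point holds, at minor severity. All three definitions condition on completing the window in which DLAEs are assessed, so a DLAE followed by exit before Day 15 is lost from numerator and denominator of the DLAE-population table. If it happens once among randomized JK07 subjects, the table shows 0/2 in place of 1/3, or 0/5 in place of 1/6. How often it would happen cannot be computed from the documents; p, q and r above are assumed.

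Two stronger readings are tempting and should not be drawn. One is that the event disappears from the report: the listing carries no completion condition, and for randomized subjects the Safety-population table keeps the event. The other is that dose escalation would rest on a depleted set: Protocol 1.1 and 4.5 have the Data Review Committee review every subject in the cohort through at least Day 15. The harm is confined to one of two descriptive tables, in a case that should be rare.

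**What to change.** In SAP V.K, define the set along these lines: *every subject given a dose of IP, sentinel subjects included, who either had a DLAE between Day 1 and Day 15 or completed DLAE follow-up through Day 15.* Basing it on dosing agrees with Protocol Table 11 and removes the nesting in the randomized-only safety population.

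Then:

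- List the subjects excluded for incomplete follow-up without a DLAE, with the reason.
- Show the DLAE rate among all dosed subjects beside the revised table. If the Safety-population table serves for this, label it as all randomized and dosed unless sentinels are included in it.
- State the downside in a footnote. With event-free early losses, the revised rate lies at or above the rate among all dosed subjects. It can also be further from the true rate than the current rule when early loss is no more likely after a DLAE than without one.
- Record the new definition under Changes from Protocol in the SAP, because it differs from Table 11.

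The cost is a reworded definition, one listing, one footnote linking the tables and one entry under Changes from Protocol. If sentinels are not in the Safety-population table, the all-dosed rate also has to be tabulated. No new data are needed, and the SAP allows changes until database lock.

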### **7.2 Subject Discontinuation/Withdrawal from the Study**

A subject may withdraw from the study at any time at his/her own request or may be withdrawn at any time at the discretion of the Investigator for safety, behavioral, compliance, or administrative reasons.

The following actions must be taken if a subject discontinues or withdraws from the study:

- If the subject withdraws consent for disclosure of future information, the Sponsor may retain and continue to use any data collected before such a withdrawal of consent.
- If a subject withdraws from the study, he/she may request destruction of any samples taken and not tested, and the Investigator must document this in the study center study records.
- See Table 1 SoA, End of Study visit (Day 180) for data to be collected at the time of study discontinuation. Should a subject request or decide to withdraw from the study prior to the End of Study visit, all efforts must be made to complete and report the observations as thoroughly as possible up to the date of withdrawal. Subjects withdrawing due to an AE at any time should be followed up until resolution, stabilization, the event is otherwise explained, the subject is lost to follow-up ([Section 8.3.8](#)) or until the end of their participation in the study. Subjects should be encouraged to complete the End of Study visit activities.
- Subjects who voluntarily withdraw will be termed dropouts. Dropouts and subjects withdrawn due to protocol violations may be replaced following discussion with the Principal Investigator and Sponsor.

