#### **9.4.5 Missing Data**

Data from subjects who withdraw from the study, including AEs and any follow-up, will be included in the analyses of all outcomes.

Missing data will be excluded from the analyses. No imputation will be performed, unless specified.

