## **B. Disposition**

The summary table of subject disposition will include all screened subjects and display the following by treatment (if applicable):

- Number of subjects who screened
- Number and percentage of subjects who failed screening with the failed inclusion/exclusion criteria as the reason of screen failure
- Number of randomized subjects
- Number and percentage of randomization failures, using the number of randomized subjects as denominator for the percentages. Randomization failure subjects are those that passed initial screening assessments and were randomized into the trial but failed out on Day 1 due to any Day 1 labs/assessments making them ineligible (e.g., they had become pregnant, lab values were unacceptable per exclusion criteria, any morning test results were exclusionary).

Subjects who discontinued the study with discontinuation reason = “Randomization Failure” on the Study Discontinuation Form will be counted as randomization failures in the summary.

- Number and percentage of subjects in each analysis population, using the number of randomized subjects as denominator.
- Number and subjects discharged later than Day 3.
- Study completion status (completed or permanently discontinued). List the number and percentage of subjects for each reason of discontinuation, using the number of randomized subjects as denominator for the percentages.
- Number of days in the study among the randomized subjects, calculated as: End of Study Date (completion or discontinuation) – IP administration date + 1.

The following termination reasons as recorded on the End of Study form will be considered:

- Adverse event
- Death
- Lost to follow-up
- Physician decision
- Study terminated by sponsor
- Subject non-compliance/protocol violation
- Withdrawal of consent

A listing will present subject enrollment, with the protocol version for which subject was enrolled, and the inclusion in each analysis population.

A separate listing by subject will display the details of screen failure reason of each subject.

A by-subject listing will display subject disposition. All randomized subjects will be included.

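### The DLAE Evaluation Population keeps only Day 15 completers, so a subject who has a DLAE and then dies or withdraws before Day 15 is missing from the table built on that set

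*SAP*

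**What the plan says.** The completer rule appears in both documents. Protocol Table 11 defines the set as "All subjects who received at least 1 dose of IP and completed the 15-day DLAE follow-up period". SAP V.K draws it from the Safety Evaluation Population and requires that subjects "have completed the 15-day DLAE follow-up period (Day 1 to Day 15").

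SAP VII then makes this the set for DLAE work: "Analyses specific to DLAEs will use the DLAE Evaluation Population". Section VII.B repeats it for the table by system organ class (SOC) and preferred term (PT): "The DLAEs will be summarized by SOC and PT for the DLAE Evaluation Population".

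Four other provisions bear on the point:

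- SAP VII.B also names DLAEs among the SOC/PT tables to be run on the Safety Evaluation Population, which has no completion requirement. It plans a separate DLAE listing as well.
- Protocol 9.4.5 states: "Data from subjects who withdraw from the study, including AEs and any follow-up, will be included in the analyses of all outcomes".
- SAP VI.B will report "Number and percentage of subjects in each analysis population, using the number of randomized subjects as denominator".
- The SAP's Safety Evaluation Population is limited to randomized subjects who were dosed. Protocol 6.3 and SAP IV.D both say that sentinel subjects are not randomized.

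**The concern.** Membership of the analysis set depends on the outcome being counted. The events that Protocol 4.6 offers as possible DLAEs include myocardial infarction, arrhythmia needing urgent intervention and toxicity of Grade 3 or worse. Any of these could end a subject's participation. If one does so before Day 15, the subject is not a completer and neither the event nor the subject is counted. Read as written, a DLAE that is fatal before Day 15 cannot appear in the DLAE-population table.

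Safety and tolerability is the primary objective, and DLAE incidence by dose is a natural summary of it. With so few subjects on JK07 at each dose, the loss of one subject can turn a dose level with a DLAE into one that shows none. The plan would also yield two DLAE tables that can differ, and it does not say which is definitive.

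**Working it through.** **Inputs.** Protocol 4.2 and the Synopsis give cohorts of 5 (one JK07 sentinel, then 3:1) to 9 (one JK07 sentinel, then 6:2), and up to 7 cohorts. The plan's only numeric design figure follows directly: 7 × 9 = 63, the stated maximum. The documents give no DLAE rate and no early-withdrawal rate, so what follows are one- and two-subject illustrations.

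**JK07 subjects per cohort, n.** Counting the sentinel, n = 1 + 3 = 4 or 1 + 6 = 7. On the SAP's literal wording, which admits randomized subjects only, n = 3 or 6.

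**Case 1: the early leaver had a DLAE.** Let x be the number of subjects with a DLAE among n dosed. All dosed subjects give x/n. The completer set gives (x − 1)/(n − 1). The shortfall is x/n − (x − 1)/(n − 1) = (n − x)/[n(n − 1)]. This is positive unless every subject had a DLAE, when both rates are 100%.

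| n | x | All dosed | Completer set | Shortfall (points) |
|---|---|---|---|---|
| 4 | 1 | 1/4 = 25.0% | 0/3 = 0% | 25.0 |
| 7 | 1 | 1/7 = 14.3% | 0/6 = 0% | 14.3 |
| 4 | 2 | 2/4 = 50.0% | 1/3 = 33.3% | 16.7 |
| 7 | 2 | 2/7 = 28.6% | 1/6 = 16.7% | 11.9 |
| 3 (randomized only) | 1 | 1/3 = 33.3% | 0/2 = 0% | 33.3 |
| 6 (randomized only) | 1 | 1/6 = 16.7% | 0/5 = 0% | 16.7 |

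**Case 2: the early leaver had no DLAE.** The completer set gives x/(n − 1), which exceeds x/n by x/[n(n − 1)]. With x = 1, 1/4 = 25.0% becomes 1/3 = 33.3% (8.3 points up), and 1/7 = 14.3% becomes 1/6 = 16.7% (2.4 points up). With x = 0 nothing changes.

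**Where the lost event still appears.** In case 1, a randomized subject's DLAE stays in the Safety-population SOC/PT table with the full denominator, so that table and the DLAE-population table disagree by the amounts above. For a sentinel this backstop fails on the SAP's literal wording: an unrandomized subject is in neither set, whether or not Day 15 was reached. Protocol Table 11 does not require randomization for the DLAE set, so the SAP is the narrower of the two here.

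**After the proposed change.** With x = 1 and the DLAE subject leaving early, the DLAE-population table shows 1/4 or 1/7, the same as all dosed subjects. Case 2 is unchanged.

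**The case against.** The strongest reply is that the event is not lost from the report. A randomized early leaver's DLAE is in the Safety-population table and should be in the DLAE listing, and the disposition table shows that the DLAE set is one subject short. The remaining defect sits in a table whose label states its restriction. This stands as a limit on the harm. It does not correct the percentage in the DLAE-population table, which SAP VII makes the set for DLAE analyses, and it does not help a sentinel.

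Second, early loss may be rare. One dose is given, stopping an infusion is not leaving the study, and subjects who withdraw because of an adverse event are to be followed up. Loss needs death or withdrawal within about two weeks. That is fair, and the documents give no rate to set against it.

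Third, Protocol 9.4.5 may be read as a general missing-data statement that operates within each defined set, since the same protocol prespecifies the completer set. That reading is reasonable, so I treat the two provisions as being in tension, not as a proven contradiction. The SAP has not departed from the protocol on the completer rule.

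**Conclusion.** The point holds in a limited form. If a dosed subject has a DLAE and then dies or withdraws before Day 15, the DLAE-population SOC/PT table understates DLAE incidence: 0/3 against 1/4 or 0/6 against 1/7 counting the sentinel, and 0/2 against 1/3 or 0/5 against 1/6 on the SAP's randomized-only wording. These figures assume exactly one DLAE subject in the group, and that this subject is the only early leaver.

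A reader might infer four stronger things, which the documents do not support:

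- **That DLAE incidence is understated in general.** The direction depends on who leaves. Early leavers without a DLAE raise the rate when another subject has one.
- **That escalation decisions are distorted.** Protocol 4.5 has the Data Review Committee (DRC) review results for all subjects in the cohort through at least Day 15. The committee does not work from this set.
- **That replacement would make the table look like a full cohort with no DLAE.** Protocol 7.2 says "Dropouts and subjects withdrawn due to protocol violations may be replaced following discussion with the Principal Investigator and Sponsor", and it uses the term dropouts for voluntary withdrawals. A death is not covered, and replacing a lost subject in a cohort of nine would need a tenth subject where nine is the stated maximum.
- **That the lack of a Day 15 onset split is an error.** The guidance criteria apply "if observed within the first 15 days of treatment (DLAE assessment period"), but Protocol 4.6 also lets the DRC designate a DLAE later. The table shells are in a separate document that was not available. This is at most a matter of clarity.

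**What to change.** In SAP V.K, define the DLAE Evaluation Population as all dosed subjects, explicitly including sentinels, who either completed Day 1 to Day 15 or had a DLAE before leaving. Because Protocol Table 11 carries the completer rule, record the change under Changes from Protocol, which now covers only vital signs. SAP I.B allows modification until database lock. After lock, the same analysis can be reported as a documented deviation in the study report.

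The cost is one clause and one line. DLAE status and adverse event start dates are already collected, so no new data are needed. The drawback is a slight upward, cautious bias: early leavers without a DLAE stay excluded while those with one are kept. With one DLAE and one such leaver this is the 8.3 or 2.4 points of case 2, which the present rule already produces.

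Optionally, show DLAEs with onset in Day 1 to Day 15 and those designated later in separate rows. This is a clarification, and the main change does not depend on it.
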